### **7.8.1. Prohibited Medications**

The following medications and treatments are prohibited during study participation:

- Any investigational agent or device other than tinostamustine, including agents that are commercially available for indications other than MM that are under investigation for the treatment of MM.
- Any anti-neoplastic treatment with activity against MM.
- Medications known to prolong the QT/QTc interval, will be excluded. The use of other concomitant medications that present a low risk of QT/QTc prolongation may be considered, with the approval of the Medical Monitor. (Refer to the crediblemeds list of drugs with known risk of TdP: <http://crediblemeds.org>.)

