## **D. Concomitant Medications**

Concomitant medication is defined as any medication with a start date within 28 days prior to the first dose of tinostamustine through Day 100 ( $\pm$  7 days). These medications will be documented as administered pre-conditioning (i.e., pre-tinostamustine); during conditioning (i.e., after the start of the first tinostamustine infusion through immediately before the start of autologous stem cell infusion); or after ASCT (i.e., after the start of ASC infusion). Any medication with a stop date prior to the first dose of study treatment is defined as a prior medication.

If the start date or the end date of a concomitant medication is missing, the following imputation rules will be applied:

Mundipharma-EDO GmbH / Protocol: EDO-S101-1004  
IQVIA Biotech (Confidential) Project # **CCI**

- For either the start or end date, if the year is missing or if the day, month, and year are all missing, do not impute.
- If both the start and stop dates are missing the month or day, the start date will be imputed first. If the imputed stop date is before the start date (imputed or non-imputed), then the stop date will be imputed using the start date.
- For the start date, if the day (or the day and the month) are missing, but all other date components match with the first dose date of study drug, use the first dose date of study drug. Otherwise, if the day (or the day and the month) are missing, but some of the other date components do not match with the first dose date of study drug, use the earliest possible date. For example, use Jan 1 if the day and the month are missing; use the first day of the actual month if only the day is missing.
- For the end date, if only the day is missing, use the last day of the month; if the day and the month are missing, use Dec 31.

Concomitant medications will be coded using the World Health Organization Drug Dictionary (WHO-DD). A separate summary table for each will be organized to display the anatomical main class (1st level) of each coded medication and, within that, the pharmacological subgroup (3rd level) of the coded medication. The summary tables will display counts and percentages of patients who reported using at least one medication in each represented pharmacological subgroup.

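### The SAP's partial-date rule for medications can move a stop recorded before dosing onto the dosing date, so a drug that had ended loses its prior classification

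*SAP*

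**What the plan says.** All the rules are in SAP section VIII.D, Concomitant Medications.

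- **Order:** "If both the start and stop dates are missing the month or day, the start date will be imputed first".
- **Start:** "if the day (or the day and the month) are missing, but all other date components match with the first dose date of study drug," the first dose date is used. Otherwise the earliest possible date is used.
- **Stop:** "For the end date, if only the day is missing, use the last day of the month; if the day and the month are missing," 31 December is used.
- **Conflict:** "If the imputed stop date is before the start date (imputed or non-imputed), then the stop date will be imputed using the start date".
- **Prior:** "Any medication with a stop date prior to the first dose of study treatment is defined as a prior medication".
- **Concomitant:** "Concomitant medication is defined as any medication with a start date within 28 days prior to the first dose of tinostamustine through Day 100", with a tolerance of one week on that visit.

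The prior definition looks at the stop and the concomitant definition looks at the start. A drug begun and ended shortly before dosing can therefore be both.

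The adverse event rules in SAP section VIII.A contain a guard that VIII.D lacks. For a fully missing onset date, the dose date is used only if the event did not end before the first dose.

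**The concern.** When a start and a stop conflict, one of the two imputed dates must be wrong. VIII.D keeps the start, which may be known only to the year, and overwrites the stop, for which the site supplied a month. Imputing a stop late is usually defended as resolving doubt towards exposure. Here there is no doubt to resolve: a stop month wholly before the dosing month means the drug ended before dosing.

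At stake are the accuracy of the derived dates and the split between prior and concomitant medication. Both summaries remain relevant: Protocol section 10.2.7 calls for both, and VIII.D keeps the definitions and the medication tables.

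**Working it through.** The SAP gives no figure to reproduce. The check applies the rules literally, reading a stop imputed using the start date as stop = start.

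**1. Worked example (dates assumed).** Dose 20 March 2019; start recorded as 2019 only; stop recorded as February 2019.

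- Start: the year matches the dose year, so start = 20 March 2019.
- Stop: only the day is missing, so stop = 28 February 2019.
- Conflict: 28 February is before 20 March, so stop = 20 March 2019.

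The latest possible true stop, 28 February, was 20 days before dosing. Before the override the record met the prior definition; afterwards it does not.

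**2. When the rule can fire.** Take any consistent record (true start on or before true stop).

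| Start as recorded | Stop as recorded | Result |
|---|---|---|
| Complete, or imputed to earliest possible date | Any partial stop | Start used ≤ true start ≤ true stop ≤ stop used: no conflict |
| Month known, equal to dosing month | Same or later month, or year only | Stop used is at or after the end of the dosing month: no conflict |
| Year only, dosing year | Year only | Stop used is 31 December of the dosing year or later: no conflict |
| Year only, dosing year | Dosing month or later | Stop used is on or after the dose date: no conflict |
| Year only, dosing year | Earlier month of dosing year | Conflict every time; stop moved to the dose date |

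Only the last row triggers the override, and in that row the drug had always ended before dosing.

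**3. Enumeration.** The same rules were run on 408,816 consistent partial-date records: 12 dose dates (the 15th of each month of an assumed year) × 167 starts × 51 durations × 4 recording patterns. The override fired in 18,224. All had a year-only start in the dosing year and a stop month before the dosing month, and all finished with start = stop = dose date although the true stop was earlier. The enumeration ignores the collection window, so 18,224 out of 408,816 is not an expected frequency in this trial.

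**4. Collection window.** Protocol section 7.8 collects medications taken from 28 days before the first dose. For a dose on day *d* of a month, the window opens on day *d* − 28.

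- If *d* is 29 to 31, the window opens within the dosing month, so no in-window stop has an earlier month.
- If *d* is 28 or less, the window reaches only into the preceding month.
- If dosing is in January, the preceding month belongs to another year and cannot be consistent with a start in the dosing year.

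In the example the window opens on 20 March − 28 days = 20 February. Only true stops from 20 to 28 February are in scope, 20 to 28 days before dosing.

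**5. What changes in the classification.** If the drug truly began within the 28 days, it is correctly concomitant by its start date and only the prior label is lost. If it began earlier, it also enters the concomitant group on a start date that is false.

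**The case against.** The strongest reply is that nothing of consequence follows. Much of that stands.

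A reader might infer that the trial would report a drug as taken on the day of tinostamustine. No specified output does so. The VIII.D tables count patients by anatomical class and pharmacological subgroup, with no dates, and a cell changes only if the patient has no other drug in that subgroup. The listing shows the eCRF entries, so the recorded partial dates should stay visible. Protocol section 7.8 also requires the date and time of medications on pharmacokinetic sampling days, which include Day -1, so dosing-day use does not rest on imputation.

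A reader might also infer false protocol violations, because Protocol section 7.8.1 says "Medications known to prolong the QT/QTc interval, will be excluded" and the memo of 30 January 2019 restricts certain anti-emetics around dosing. Deviations, however, are recorded in the trial management system (SAP section VI.C; memo of 21 September 2018, Item 4). Nothing derives them from imputed medication dates.

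Nor do the documents support an effect on dose-limiting toxicities or QTcF. SAP section I.C withdraws the analysis of their number and frequency. QTcF is read centrally from Holter recordings under a separate ECG plan (Protocol sections 9.2.5 and 9.2.6), and no specified analysis links it to imputed medication dates.

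What the reply does not remove is that a stated rule overrides a recorded month and defeats the SAP's own prior definition.

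**Conclusion.** The point holds as a minor defect in a derivation rule. For internally consistent records, every time the override fires it gives a stop date that contradicts the record and removes a prior classification that was correct. It does not follow that every affected drug is wrongly called concomitant, because one begun within 28 days before dosing belongs there by its start date.

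The number of records is unknown and probably small. The trigger needs a year-only start in the dosing year together with a stop known to the month just before dosing. This assumes that sites record only medications within the 28-day window. The consequence is limited to derived start and stop dates and the prior and concomitant summary tables. No conclusion of the study is shown to depend on it.

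**What to change.** Make three changes in SAP section VIII.D. Changing the conflict sentence alone would not be enough, because the start-date bullet would still place the start on the dose date.

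1. Replace the conflict sentence with: *A stop date is never moved outside its recorded month or year.*
2. Add to the start-date bullet: *The first dose date is not used for a partial start when the recorded or latest possible stop date is before the first dose; use the earliest possible date consistent with the recorded components instead.*
3. Add: *Such a medication is classified as prior from its stop date. The imputed earliest start is not used to remove it from the concomitant (pre-conditioning) table when the recorded components allow a start within 28 days before dosing.*

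The third change is needed because a start imputed to 1 January could otherwise drop a drug truly begun inside the 28-day window. The second also closes a related gap. A complete stop before dosing, with a partial start imputed to the dose date, now leaves the start after the stop, because the conflict sentence covers only imputed stops.

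The cost is a small SAP and programming change, and a few drugs begun before the 28-day window may stay in the concomitant table. SAP section I.B allows modification until database lock; after that, the change can be documented in the study report.

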## IX. Pharmacokinetic Analyses

Pharmacokinetic data are not within the scope of this SAP. These data will be reported by a third-party vendor and their analysis described in a separate report.

## X. References

Please refer to the References section of the Mundipharma-EDO GmbH EDO-S101-1004 protocol for all referenced items in the analysis plan, as well as other supportive materials.
